1.4 Study design

This is an international, multicentre, double-blind, randomised, parallel-group, placebo-controlled Phase III study to evaluate the effect of ticagrelor versus placebo in reducing the rate of VOCs in paediatric patients with SCD (Figure 1). During the treatment period, patients will be monitored for occurrence of VOCs and other acute SCD complications.

Study participants should receive standard of care for SCD, adjusted to the individual patient at the discretion of the Investigator, including routine health care screening examinations and immunisations according to local guidelines and health care programmes. Study drug will be given on the background of standard treatments for SCD. However, restrictions apply to some medications and interventions that may be necessary for the patient's health and well-being during the study. Temporary hold of study drug dosing could therefore be needed in case of short-term treatment with a medication not to be combined with study drug or in case of surgical interventions. Patients are to be followed for up to 24 months or until a common study end date (CSED) is reached defined as 12 months after the last patient is randomised. The target population are children aged ≥ 2 to < 18 years of age and body weight of ≥ 12 kg diagnosed with HbSS or HbS/ β^0 . At least 50 evaluable patients should be recruited in each of the age groups, ≥ 2 years to < 12 years and ≥ 12 years to < 18 years.

Figure 1 Study Flow Chart

bd Twice a day; d Day; EOS End of study; mo Month; R Randomisation; wk Week

^a Patients randomised to ticagrelor will receive doses based on weight band (at Screening): ≥ 12 to ≤ 24 kg=15 mg, >24 to ≤ 48 kg=30 mg, >48 kg=45 mg.

^b EOS = Patients will be followed to common study end date defined as 12 months after the last patient is randomised, or up to 24 months.

^c See [Table 2](#) for assessments during site visits and [Table 3](#) for telephone visits that will occur monthly after Week 4 between site visits.

^d Interval must not be more than 100 days to ensure tablet supply for all days.

NB. Only on-site visits are shown.

1.5 Study governance and oversight

1.5.1 Steering Committee

A Steering Committee (SC) has been appointed for this study and has provided expert advice on, eg, the overall design, including the development of the protocol. The SC will continue to advise on any protocol amendments and will monitor study conduct, result interpretation and reporting of the study. The SC can propose to AstraZeneca their recommendations regarding study modifications or a potential early stop to the study based on the information received from the DMC. The SC is comprised of designated international academic leaders and non-voting members of the Sponsor, and will operate under a SC charter.

The Sponsor has the overall responsibility of the study.

1.5.2 Data Monitoring Committee

A DMC composed of independent SCD paediatric experts and including a platelet expert and statistician, will be appointed for this study and will report to the SC. The DMC will be responsible for safeguarding the interests of the patients in the study by assessing the safety of the intervention during the study, and for reviewing the overall conduct of the clinical study. The DMC will have access to unblinded individual data and be able to evaluate these while the study is ongoing. The DMC meeting schedule is shown in [Table 1](#). Additional meetings could be initiated by the DMC chair or the Sponsor as needed.

The DMC will consider recommending study termination for any episode of bleeding deemed related to the ticagrelor treatment that is fatal, or is a spontaneous intracranial haemorrhage, or if the accumulating data suggest a strong likelihood of excessive haemorrhagic events possibly related to ticagrelor that require medical intervention as reported by the Investigator. Study termination will also be considered if the number of fatal or life-threatening serious adverse events (SAEs), including but not limited to bleedings, is greater in ticagrelor-treated patients compared to placebo.

The DMC will make recommendations on the progression of the study based on the totality of data (eg, AEs, safety laboratory variables, ticagrelor exposure and platelet inhibition) or other findings putting patients at undue risk. The Sponsor has the final decision on study progression including amendments, etc.

Additionally, the DMC will do a formal interim PD assessment when 60 patients have had their PK/PD sampling after 4 weeks in the study. In this interim PD assessment, the mean of pre-dose and 2 hours post dose PRI values at 4 weeks will be calculated for each individual and compared to their respective baseline values. The population mean of the platelet inhibition in the ticagrelor arm is expected to be above 35% during the study. If there is a risk of not achieving the targeted inhibition level of 35% to 80% in the study, the first task of the DMC would be to investigate if the PK values and the PK/PD relationship are as expected and in line with earlier documented PK/PD data of ticagrelor. If any finding is deemed by the DMC to not be in accordance with expected PK and PD data and all other reasons for the unexpected findings are ruled out, they will contact the Sponsor and ask for proof of treatment

compliance and potentially escalate the issue the Steering Committee regarding a potential amending of the study in order to evaluate the need for a dose change based on new modelling and simulations including the new data.

A DMC charter will be prepared to detail precise roles and responsibilities and procedures to ensure maintenance of the blinding and integrity of the study in the review of accumulating data and interactions with the SC.

Evaluation	Number of patients randomized	Completed visit (months)
1	40 patients completed Visit 4 or 10 patients completed Visit 6	4 (1) or 6 (3)
2	60 patients (formal interim PD assessment)	4 (1)
3	80 patients	6 (3)
4	80 patients	9 (6)
5	All patients	4 (1)
6	All patients	9 (6)
x	Patients remaining in study	As needed ^a

^a As deemed necessary by the DMC chair and/or Sponsor.
PD pharmacodynamic.

2. STUDY OBJECTIVES

A VOC is the composite of a painful crisis and/or an ACS ([Howard et al 2015](#), [Yawn et al 2014](#)). Each component is defined as:

A painful crisis is an onset or worsening of pain that lasts at least 2 hours, for which there is no explanation other than vaso-occlusion and which requires therapy with oral or parenteral opioids, parenteral non-steroidal anti-inflammatory drugs (NSAIDs), or other analgesics prescribed by a health care provider in a medical setting (such as a hospital, clinic, or emergency room visit) or at home.

An ACS is an acute illness characterized by fever and/or respiratory symptoms, accompanied by a new pulmonary infiltrate on a chest X-ray.

2.1 Primary objective

Primary Objective:	Outcome Measure:
To compare the effect of ticagrelor vs placebo for the reduction of VOCs, which is the composite of painful crisis and/or ACS, in paediatric patients with SCD	Number of VOCs

2.2 Secondary objectives

Secondary Objective:	Outcome Measure:
To compare the effect of ticagrelor vs placebo for the reduction of painful crises	Number of painful crises
To compare the effect on ticagrelor vs placebo for the reduction of ACS	Number of ACSs
To compare the effect of ticagrelor vs placebo for the reduction of duration of painful crises	Duration of painful crises
To compare the effect of ticagrelor vs placebo on the number of VOCs requiring hospitalisation or emergency department visits	Number of VOCs requiring hospitalisation or emergency department visits
To compare the effect of ticagrelor vs placebo on reduction of days hospitalised for VOC	Number of days hospitalised for VOC
To compare the effect of ticagrelor vs placebo on the number of acute SCD complications ^a	Number of acute SCD complications
To compare the effect of ticagrelor vs placebo on reduction of days hospitalised for acute SCD complications ^a	Number of days hospitalised for acute SCD complications
To compare the effect of ticagrelor vs placebo on the number of sickle cell-related red blood cell (RBC) transfusions	Number of sickle cell-related RBC transfusions
To describe the health-related quality of life (HRQL) and fatigue	HRQL total score and by dimension using Paediatric Quality of Life Inventory (PedsQL) SCD Module and Fatigue total score and by dimension using the PedsQL Multidimensional Fatigue Scale as presented in Appendix I (age appropriate versions)
To describe absence from school or work due to SCD	Proportion of days of absence from school or work (only if going to school or work at randomisation)
To describe intensity of pain during VOC	Intensity of worst pain daily during VOC - For patients ≤ 4 years of age, observer reported using the Face, Legs, Activity, Cry, Consolability Scale (FLACC) - For patient ages 5 to 18 years of age, self-reported using the Faces Pain Scale Revised (FPS-R)
To describe analgesics use during VOC	Type of analgesics (opioid and non-opioid) use

To describe patient acceptability of the formulation (palatability and swallowability)	
 - For patients ≤ 4 years of age taking the tablet dispersed or whole, an observer assessment of palatability and swallowability will be undertaken - For patients ≥ 5 years of age taking the tablet dispersed or whole, palatability will be assessed and categorised using the Facial Hedonic Scale
--	--

^a The acute SCD complications are defined in Section 5.1.5.

2.3 Safety objectives

Safety Objective:	Outcome Measure:
To assess long-term safety and tolerability of therapy with ticagrelor vs placebo	AEs/SAEs, including bleeding Vital signs and laboratory safety variables

2.4 Exploratory objectives

Exploratory Objective:	Outcome Measure:
To compare the effect of ticagrelor vs placebo for the reduction of duration of ACS	Duration of ACS
To assess the pharmacokinetics (PK) of ticagrelor and AR-C124910XX in paediatric patients with SCD using a population PK model	Population PK parameters such as oral clearance (CL/F) and ticagrelor exposure (AUC) Observed plasma concentrations of ticagrelor and the active metabolite AR-C124910XX
To assess the effect of ticagrelor on platelet aggregation	PRI measured by vasodilator-stimulated phosphoprotein (VASP) assay

3. SUBJECT SELECTION, ENROLMENT, RANDOMISATION, RESTRICTIONS, DISCONTINUATION AND WITHDRAWAL

Each patient must meet all of the inclusion criteria and none of the exclusion criteria for this study. Under no circumstances can there be exceptions to this rule.

3.1 Inclusion criteria

For inclusion in the study, patients must fulfil the following criteria:

1. Provision of signed and dated informed consent prior to any study specific procedures not part of standard medical care (local regulations and international guidelines are to be followed in determining the assent/consent requirements for children).
2. Male or female paediatric patients aged ≥ 2 to < 18 years and body weight of ≥ 12 kg (at Visit 1), diagnosed with HbSS or HbS/ β^0 as confirmed by high-performance liquid

chromatography or haemoglobin electrophoresis.

Note: Diagnosis of SCD (if not confirmed prior to screening and records available on the medical file) should be confirmed for HbSS or HbS/ β^0 by high-performance liquid chromatography or haemoglobin electrophoresis, performed at the site's local lab, in order to confirm the type of mutation.

3. Have experienced at least 2 VOCs (painful crisis and/or ACS) as judged by the Investigator in the past 12 months prior to Visit 1. These VOCs need to be documented in the patient's medical records or in other documents that can be reconciled.
4. If ≤ 16 years old, must have had transcranial Doppler (TCD) within the past year prior to Visit 1. If this is not the case, a TCD examination must be done before proceeding in the study.
5. If ≥ 10 years old, must have had an ophthalmological examination within the past year prior to Visit 1. If this is not the case, the patient must be examined by an ophthalmologist before proceeding in the study. If local guidelines dictate ophthalmological examination at younger ages, those local guidelines should be followed.
6. If treated with hydroxyurea, the weight-adjusted dose must be stable for 3 months before screening.
7. Suitable venous access for the study-related blood sampling
8. Prior to dosing on day of randomisation (Visit 2), a negative urine (dipstick) pregnancy test performed at Screening (Visit 1) and at Visit 2 must be available for female patients of childbearing potential.
9. Females of childbearing potential (after menarche) must not become pregnant during study. Sexually active females must use a highly effective method of contraception which results in a low failure rate (ie, less than 1% per year). If use of effective contraception cannot be secured in sexually active females, the patient cannot be included in this study. Refer to Section 3.8 for highly effective methods of contraception.

3.2 Exclusion criteria

Patients should not enter the study if any of the following exclusion criteria are fulfilled:

1. History of transient ischaemic attack (TIA) or cerebrovascular accident (ischaemic or haemorrhagic), severe head trauma, intracranial haemorrhage, intracranial neoplasm, arteriovenous malformation, aneurysm, or proliferative retinopathy.
2. Findings on TCD: Current or previous values for time averaged mean of the maximum velocity (TAMMV) that are Conditional or Abnormal. Patients with Conditional TAMMV values or higher (≥ 153 cm/sec using TCD imaging technique [TCDi] which is corresponding to ≥ 170 cm/sec by the non-imaging technique). Both the middle cerebral artery and the internal carotid artery should be considered. Any other criteria that would locally be considered as TCD indications for chronic transfusion would also exclude the patient.
3. Active pathological bleeding or increased risk of bleeding complications according to Investigator
4. Haemoglobin < 6 g/dL from test performed at Screening (Visit 1)
5. Platelets $< 100 \times 10^9/L$ from test performed at Screening (Visit 1)
6. Undergoing treatment with chronic red blood cell transfusion therapy

7. Chronic use of NSAIDs defined as continuous intake >3 days per week that cannot be discontinued
8. Receiving chronic treatment with anticoagulants or antiplatelet drugs that cannot be discontinued
9. Moderate or severe hepatic impairment defined as laboratory values of alanine aminotransferase (ALT) >2 × upper limits of normal (ULN), total bilirubin >2 × ULN (unless judged by the Investigator to be caused by haemolysis), albumin <35 g/L (3.5 g/dL) and International normalised ratio (INR) >1.4, or symptoms of liver disease (eg, ascites) from test performed at Screening (Visit 1).
10. Renal failure requiring dialysis
11. Patient considered to be at risk of bradycardic events (eg, known sick sinus syndrome or second or third-degree atrioventricular block) unless already treated with a permanent pacemaker.
12. Concomitant oral or intravenous therapy with strong cytochrome P450 3A (CYP3A) inhibitors, CYP3A substrates with narrow therapeutic indices, or strong CYP3A inducers (see full list in [Appendix G](#)), which cannot be stopped at least 5 half-lives before randomisation.
13. Active untreated malaria. Patients with suspected malaria at Screening (Visit 1) will be tested.
14. Known hypersensitivity or contraindication to ticagrelor
15. Patients who are currently pregnant or breastfeeding, or planning to become pregnant during the study or have given birth less than 3 months prior to Screening (Visit 1)
16. Any condition which, in the opinion of the Investigator, would make it unsafe or unsuitable for the patient to participate in this study
17. Concern for the inability of the patient or caregiver (defined as legally authorised representative) to comply with study procedures and/or follow-up
18. Previous randomisation in the present study
19. Participation in another clinical study with an IP or device during the last 30 days preceding screening.
20. Involvement of member of patient's family, or patient self, in the planning and/or conduct of the study (applies to both AstraZeneca staff and/or staff at the study site).

Procedures for withdrawal of incorrectly enrolled patients see Section 3.3.

3.4 Procedures for handling incorrectly enrolled or randomised subjects

Patients who fail to meet the eligibility criteria must not, under any circumstances, be enrolled or receive IP. There can be no exceptions to this rule. Patients who are enrolled, but subsequently found not to meet all the eligibility criteria must not be randomised or initiated on treatment, and must be withdrawn from the study.

Where a patient does not meet all the eligibility criteria but is randomised in error, or incorrectly started on treatment, the Investigator should inform the AstraZeneca Study Physician or representative immediately, and a discussion should occur between the AstraZeneca Study Physician and the Investigator regarding whether to continue or discontinue the subject from treatment. The AstraZeneca Study Physician or representative must ensure all decisions are appropriately documented.

In those cases where continuation of study therapy is judged not to present a concern related to safety and disease management, the rationale for continuing study therapy must be clearly documented. The patient should continue follow-up in accordance with defined study procedures.

3.5 Methods for assigning treatment groups

The randomisation codes will be computer generated by AstraZeneca R&D and loaded into the IXRS database. Randomisation codes will be generated in blocks to ensure approximate balance (1:1) between the 2 treatment arms (ticagrelor or placebo bd). Stratification for baseline hydroxyurea use by country will be applied.

For each patient randomised the IXRS will provide the Investigator with a unique kit ID number matching the treatment arm assigned to the patient. Following randomisation, the first dose of study drug will be administered to the patient as soon as possible. At randomisation and subsequent dispensing visits, the patient should always be provided medication with the kit ID(s) allocated by the IXRS. If a patient receives the incorrect randomised treatment at any time during the study, this must be corrected as soon as discovered after discussing with the Study Physician.

3.6 Methods for ensuring blinding

This is a double-blind study. Ticagrelor and matching ticagrelor placebo tablets will be identical in appearance and packaging. The bottles with IPs will be labelled with unique ID numbers allocated from the IXRS, but it will not indicate treatment allocation.

No member of the study team at AstraZeneca or representative, personnel at study centres or any contract research organisation (CRO) handling data will have access to the randomisation scheme during the conduct of the study, with the exception of the AstraZeneca personnel generating the randomisation scheme and the bioanalysis personnel analysing the pharmacokinetic (PK) samples as well as AstraZeneca Supply Chain, the Patient safety data entry site and the CRO companies providing the IXRS and carrying out the packaging and labelling of IPs. This documentation will be kept in a secure location until the end of the study.

There will be an independent, unblinded statistical team that will support the DMC with data during the study. Personnel involved in the clinical study at AstraZeneca or representative will remain blinded to these analyses and will have no knowledge of the results presented to the DMC.

3.7 Methods for unblinding

Individual treatment codes, indicating the treatment randomisation for each randomised patient, will be available to the Investigator(s) or pharmacists from the IXRS. Routines for this will be described in the IXRS user manual that will be provided to each centre.

The treatment code should not be broken except in medical emergencies when the appropriate management of the patient requires knowledge of the treatment randomisation. The Investigator documents and reports the action to AstraZeneca, without revealing the treatment given to patient to the AstraZeneca or representative staff. The number of individuals at the study site who become aware of the treatment status should be kept to an absolute minimum including keeping the patient blinded if possible. Treatment with study drug should be continued if considered appropriate.

AstraZeneca retains the right to break the code for SAEs that are unexpected and are suspected to be causally related to an IP and that potentially require expedited reporting to regulatory authorities. Treatment codes will not be broken for the planned analyses of data until all decisions on the evaluability of the data from each individual patient have been made and documented.

3.8 Restrictions

The following restrictions will be applied for patients participating in the study:

1. Patients may not participate in another clinical study that involves an IP (active or placebo) or device during this study.

2. Females of childbearing potential (after menarche) must not become pregnant. Sexually active females of childbearing potential must use a highly effective method of contraception, which results in a low failure rate (ie, <1% per year) from enrolment to the follow-up visit. If this cannot be secured, the patient cannot continue in this study. Examples of highly effective methods include implants, injectables, combined oral contraceptives, some intrauterine devices, or vasectomized partner. For male study participants, there are no restrictions against fathering a child when treated with ticagrelor.
3. For concomitant medications which are restricted during the study, see [Appendix G](#).
4. If the patient is receiving digoxin, levels should be monitored closely following initiation of IP and with any change in IP, see [Appendix G](#).
5. Intake of grapefruit juice is not allowed.
6. Patients should participate in annual ophthalmological and TCD examinations in age groups according to guidelines.
7. On visits with PK or vasodilator stimulated phosphoprotein (VASP) sampling, the morning dose of IP should not be taken at home. The dose will be administered at the site. See [Table 2](#) for study assessment schedule, and Sections [5.4.1](#) (PK) and [5.5.2](#) (VASP).

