3.9 Permanent discontinuation or temporary stop of investigational product

3.9.1 Permanent discontinuation

Patients may be permanently discontinued from IP in the following situations:

1. The patient (or caregiver) is at any time free to discontinue treatment or advise the patient to discontinue treatment, without prejudice to further treatment
2. AE, as judged by Investigator, that with continued treatment would put the patient at undue risk
3. Severe non-compliance with the study protocol, as judged by Investigator and/or AstraZeneca
4. Severe illness or risk to the patient as judged by the Investigator
5. Any major bleeding, for bleeding definitions see Section [6.3.8](#).
6. Repeated minor bleedings not needing medical intervention unless clearly not related to study drug (eg, minor trauma during playing), as judged by the Investigator
7. For females of childbearing potential, who are sexually active and where effective contraception cannot be secured, the study treatment must be discontinued
8. In the event of pregnancy, study drug should be immediately permanently discontinued. The patient is encouraged to continue to be followed in the study according to the study plan.
9. Conditional or Abnormal TCD findings, ie, TAMMV values are ≥ 153 cm/sec using TCDi technique (corresponding to ≥ 170 cm/sec by the non-imaging technique), indicating an increased risk of stroke.
10. Pathological findings on any imaging technique indicating increased risk of ischaemic or haemorrhagic stroke
11. TIA or stroke (ischaemic or haemorrhagic)
12. Need for chronic transfusion therapy
13. Findings indicating impaired liver function and/or coagulopathy:

- ALT or aspartate aminotransferase (AST) $>5 \times \text{ULN}$, ALT or AST $>3 \times \text{ULN}$ and total bilirubin level $>2 \times \text{ULN}$ (unless bilirubin increase clearly explained by haemolysis), INR >1.5 . For potential Hy's Law laboratory criteria: the elevation in transaminases must precede or coincide with (ie, on the same day as) the elevation in total bilirubin, but there is no specified timeframe within which the elevations in transaminases and total bilirubin must occur.

14. Renal failure requiring dialysis
15. Patients with clinical symptoms of bradyarrhythmia as judged by the Investigator and/or ECG findings of significant sinus pauses or high degree atrioventricular block
16. Development of proliferative retinopathy.

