3.9.2 Temporary discontinuation

Patients may be temporarily discontinued from IP in the following situations:

1. Clinically significant thrombocytopenia (platelet count $<80 \times 10^9/\text{L}$) which mandates an interruption of IP due to patient safety in the assessment of the Investigator. Repeat laboratory studies and standard of care should be followed until resolution of laboratory abnormality and if deemed appropriate, the IP can be restarted when platelet counts are $>100 \times 10^9/\text{L}$.
2. Major or minor surgery or invasive procedures, for example, intramuscular injections. The IP should be temporary stopped 5 days prior to the procedure and can be restarted when bleeding risk is considered low, as judged by the Investigator.
3. Temporary need of treatment with prohibited concomitant medications, see [Appendix G](#). The IP may be interrupted temporarily at the discretion of the Investigator; however, such cases are recommended to be discussed with the IQVIA Study Physician and the Sponsor Physician as soon as the Investigator is aware.
4. Novel coronavirus (COVID-19) pandemic, see Section [3.9.4](#).

Discontinuation of IP does not mean discontinuation of follow-up or termination of study participation. Study assessments should continue in all cases if possible.

If patients are not willing to come back to study visits, the sites are encouraged to investigate patient barriers to study visit compliance and discuss with the Clinical Research Associate (CRA) if there is any alternative follow-up schedule which can meet patient expectations. Prior to implementing alternative follow-up schedules, AstraZeneca approval must be granted.

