3.9.3 Procedures for permanent discontinuation of a subject from investigational product

At any time, patients are free to discontinue IP, without prejudice to further treatment. A patient that decides to discontinue IP will always be asked about the reason(s) and the presence of any AEs. Adverse events (AEs) will be followed up (see Section [6](#)) and all IPs should be returned by the patient. Patients permanently discontinuing IP should always be asked to continue the regular visits. It is essential to collect as much data as possible for all patients throughout the study and especially all potential endpoint events. Complete

withdrawal from the study (withdrawal of consent) has a direct negative impact on the potential validity of all study data and should be avoided wherever possible.

If patients are not willing to come back to study visits, the sites are encouraged to investigate patient barriers to study visit compliance and discuss with the CRA if there is any alternative follow-up schedule which can meet patient expectations. Prior to implementing alternative follow-up schedules, AstraZeneca approval must be granted.

If a patient is withdrawn from study, see Section 3.10.

3.9.4 Procedures and guidance for temporary IP discontinuation in relation to coronavirus disease 2019 (COVID-19)

If a patient is diagnosed with COVID-19 or is suspected to have COVID-19 and an AE/SAE is reported (see Section 6.3.10), the Investigator should determine whether the patient's IP administration should continue or be temporarily discontinued. Patients who are discontinued from IP due to COVID-19 are to remain in the study whenever possible for safety follow-up.

In case a patient is unable to attend on-site visits for undergoing safety-related assessments as detailed in the Schedule of Assessments (Table 2), due to local public health rules, patient inability or patient/caregiver decision, the patient must be temporarily discontinued from IP, unless the safety-related assessments (including vital signs, physical examination, blood samples for safety laboratory assessments, urine for urinalysis, eDevice review, ECGs, VOCs, and recording of concomitant medications and AEs) can be performed at the patient's home and/or local laboratories or other local facilities by delegated site staff.

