3.10.2 Withdrawal of the informed consent

Patients are free to withdraw from the study at any time (ie, permanent discontinuation of IP and study schedule assessments), without prejudice to further treatment.

Withdrawal of consent from the study must be documented by the Investigator in the patient medical records and recorded in the electronic case report form (eCRF) as well as in the Informed Consent Form (ICF). The reason for permanent discontinuation of IP, the date of the last dose of the IP, reason for withdrawal and the presence of any AEs must be documented in the eCRF. The Investigator will follow-up AEs outside of the clinical study. The patient will return the electronic device (eDevice).

If a patient withdraws from participation in the study, then his/her enrolment/randomisation code cannot be reused. Withdrawn patients will not be replaced after randomisation.

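### Protocol 3.8 and 3.9.1 give different consequences when contraception cannot be secured, so a randomised patient's VOC follow-up depends on which section a site follows

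*Protocol*

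**What the plan says.** Protocol 3.8 item 2 restricts sexually active females of childbearing potential to a highly effective contraceptive method, described as a failure rate below 1% per year. The restriction applies "from enrolment to the follow-up visit", so it covers patients after randomisation as well as at entry. Its consequence is "If this cannot be secured, the patient cannot continue in this study".

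Protocol 3.9.1 lists grounds for permanent discontinuation of the investigational product. Item 7 covers sexually active females of childbearing potential and reads "where effective contraception cannot be secured, the study treatment must be discontinued". It does not mention leaving the study. Item 8, on pregnancy, stops the drug and adds: "The patient is encouraged to continue to be followed in the study according to the study plan".

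Two further sections deal with what happens after the drug is stopped. Section 3.9.2 states: "Discontinuation of IP does not mean discontinuation of follow-up or termination of study participation". Section 3.9.3 states: "Patients permanently discontinuing IP should always be asked to continue the regular visits". It also says that complete withdrawal "has a direct negative impact on the potential validity of all study data and should be avoided wherever possible".

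Section 3.10 provides for screen failure and withdrawal of consent only. Under 3.10.2, "Withdrawn patients will not be replaced after randomisation".

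Protocol 8.5.1 and SAP Appendix E define the primary analysis under a treatment-policy estimand. Events after drug discontinuation count, and observation stops at study withdrawal, after which data are assumed missing at random.

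**The concern.** A single on-study finding leads to two different instructions. Contraception is reviewed at on-site visits (Protocol 4.2.1) and recorded or considered at the monthly telephone visits (4.2.2 and Appendix E), so sites will be looking for this trigger. Nothing in the protocol says which section prevails.

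What is at stake is the primary endpoint. A treatment-policy analysis needs VOCs to be observed after the drug stops. If a site reads 3.8 literally, the patient's later VOCs are never observed, although 3.9.1 and 3.9.3 would have kept her under observation. The gap would then be filled implicitly by the missing-at-random assumption. For a ticagrelor patient, the unobserved time would be time off drug, while the model carries forward a rate estimated largely from time on drug. If ticagrelor works and its effect fades after stopping, that assumption leans towards ticagrelor for those patients.

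**Working it through.** **Provisions side by side**

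| Protocol section | Trigger | Stated consequence |
|---|---|---|
| 3.8 item 2 | Highly effective method not secured, enrolment to follow-up visit | Patient does not continue in the study |
| 3.9.1 item 7 | Effective contraception not secured | Study treatment stops; follow-up not mentioned |
| 3.9.1 item 8 | Pregnancy | Drug stops; follow-up encouraged |
| 3.9.2 | Drug stopped (under the temporary heading, but worded generally) | Follow-up and participation do not end |
| 3.9.3 | Drug permanently stopped | Patient asked to keep regular visits |
| 3.10 | Screen failure or withdrawn consent | No entry for a removal under 3.8 |

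Take a girl randomised with secured contraception in whom it later cannot be secured. Under 3.8 she leaves the study, and her follow-up time in the model ends there. Under 3.9.1 item 7 with 3.9.3 she stops drug, is asked to stay, and her VOCs count to the end of her treatment period. Inclusion criterion 9 already handles entry, so 3.8 cannot be read as an entry rule alone.

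**The SAP's handling of such a withdrawal**

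The pDRMI text in Appendix E treats development of study-specified reasons as treatment related, and ticagrelor patients then receive the placebo rate. Table 7 repeats this for withdrawal from the study. Table 6, on stopping treatment, has a row for study-specific discontinuation criteria. Table 5, on withdrawing from the study, does not. A ticagrelor patient removed under 3.8 therefore has no default row. A placebo patient is unaffected, because placebo patients always receive the placebo rate.

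**The plan's own sample size**

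Inputs from Protocol 8.2: shape 0.8, so dispersion k = 1/0.8 = 1.25; rates 2.0 and 1.0 per year; 154 patients (77 per arm); mean follow-up 18 months; two-sided 5%. Information per patient on the log rate is mu/(1 + k·mu).

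- At 1.5 years: placebo mu = 3, information 3/4.75 = 0.632. Ticagrelor mu = 1.5, information 1.5/2.875 = 0.522.
- SE = sqrt((1/0.632 + 1/0.522)/77) = sqrt(3.50/77) = 0.213.
- Power = Phi(0.693/0.213 − 1.96) = 90.2%.
- With follow-up uniform on 12 to 24 months the formula gives 89.95%, and a 1,500-run simulation gives 90.3%. The stated figure of about 90% is reproduced.
- The increase from 154 to 182 implies a dropout allowance of 1 − 154/182 = 15.4%.

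**Power if some patients are cut short**

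This illustration uses the same formula, 182 patients and uniform follow-up. The affected patients are assumed to be observed for 6 months only and spread evenly over the arms.

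| Patients cut to 6 months | Power |
|---|---|
| 0 | 94.07% |
| 1 | 94.03% |
| 5 | 93.87% |
| 10 | 93.65% |

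**How many patients**

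The documents give no count. Assume half of the 182 are female, 40% to 60% of these are past menarche, and contraception cannot be secured at some point in 2% to 10% of those.

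- 182 × 0.5 × 0.4 = 36 and 182 × 0.5 × 0.6 = 55 girls at risk.
- 36.4 × 0.02 = 0.7 and 54.6 × 0.10 = 5.5 patients, or about 0.4% to 3% of the trial.

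**The case against.** The strongest reply is that one sentence in a list of restrictions would not override the sections that actually govern stopping. Sections 3.9.1 to 3.9.3 all favour continued observation, a note to Table 2 lets telephone contacts replace site visits once drug is stopped, and 3.10 gives no procedure for a removal under 3.8. This stands in part. A reader might infer that randomised girls do lose VOC follow-up under this protocol, but the documents show only that they would at a site that follows 3.8.

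A reader might also infer that 3.9 obliges follow-up to continue, or that the two items differ on follow-up alone. Neither is supported. Section 3.9.3 says patients should be asked, item 8 says encouraged, and 3.9.2 qualifies continued assessments with *if possible*. The triggers also differ: 3.8 says highly effective and item 7 says effective. Inclusion criterion 9 uses both terms, so they may be meant alike, but the text does not say so. Section 3.9.1 also opens with *may* while item 7 says *must*.

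The plan does have tools for a few withdrawals: pDRMI, DRMI, a tipping-point analysis if the primary result is favourable, and patient-level review before unblinding. This limits the damage. However, SAP 4.2.6.3 says the missing-data analyses may be conducted, not that they will be, and Table 5 lacks the row that would classify these cases.

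Finally, the SAP records that the sponsor ended the study early (3.1.4.1), so an amendment may no longer recover any follow-up. That is fair. It does not affect the identification and classification of patients already removed.

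**Conclusion.** The contradiction stands on the text, and no other section resolves it. Its consequence is conditional: avoidable missing primary-endpoint data at sites that follow 3.8, and none from this cause where 3.9.1 and 3.9.3 are followed and the patient agrees to stay.

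The size is probably small. The range of about 1 to 5 patients rests wholly on assumed proportions, and the effect on power is negligible even at 10 patients. A reader might infer a loss of up to 24 months for each patient. That is only a ceiling, because criterion 9 excludes girls whose contraception is unsecured at entry, so any loss begins after randomisation, and planned mean follow-up is 18 months. Nor do the documents support a claim of bias in a planned subgroup of adolescent girls: SAP 4.2.6.4 examines age and gender separately.

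The case rests on site-dependent missing data that the protocol itself says should be avoided. It does not rest on power, or on a view that either contraception rule is the right one.

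**What to change.** 1. Reconcile Protocol 3.8 item 2 with 3.9.1 item 7, including highly effective versus effective. Which contraception and drug-stopping rule applies is for the sponsor and its clinical advisers; this review does not choose one.
2. State in 3.8 that, for patients already randomised, VOC outcome follow-up continues under 3.9.3 unless consent is withdrawn. Entry under inclusion criterion 9 stays as it is.
3. At the SAP's existing review before unblinding, identify any patient removed under 3.8 and document the imputation category assigned to her under pDRMI and DRMI. A row in Table 5 for this reason would close the gap.

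The cost is a sentence or two in a protocol amendment and one table row in the SAP. No visits are added beyond the schedule. With the study terminated early, the first two items may only tidy the record, but the third can still be done before database lock.
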